9.0 TREATMENT/INTERVENTION PLAN

- Patients who are randomized to the intervention arm of our study will undergo planned laparotomy with routine primary closure of their surgical incision at the completion of the case. Staples will be used for skin closure after standard fascial closure with PDS suture.
- Immediately thereafter, the experimental Prevena Therapy System will be applied to the closed, clean or clean-contaminated surgical incision.
- The Prevena[™] Customizable[™] dressing will then be connected to the Prevena 125 Therapy Unit to maintain a constant negative pressure of -125 mmHg.
- The Prevena system will be left on for a minimum of 2 days and up to a maximum of 7 days while the patient remains in the hospital post-operatively.
- All Prevena systems will be removed on the day of discharge or post-operative day 7, whichever occurs first.
- Evaluation for wound complications will be performed through provider-completed data collection sheets. These evaluations will be performed on the day of discharge (or POD 7 at the time of Prevena system removal) and at the patient's routine post-operative visit, which will occur at 30 days +/- 5 days after the day of surgery.
- Ongoing evaluation and documentation via phone calls, urgent care visits and nursing follow-up are in place to collect information throughout this time period as per institutional guidelines.
- Patients who are unable to return for their post-operative visit before POD 35 will be contacted via telephone by a study investigator to complete a wound assessment based on what the patient reports.
- Patient follow-up will cease at the time an "event" is documented even if it occurs prior to the planned 30-day follow-up period. An event refers to one of the following:
 - Wound infection
 - Wound separation
 - \circ Wound seroma
 - \circ Wound hematoma

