4.0 OVERVIEW OF STUDY DESIGN/INTERVENTION

4.1 Design

This is a randomized phase III study of patients undergoing laparotomy for either gynecologic malignancies or any indication in patients with a BMI \geq 40. At Hartford Healthcare, this study will be performed on gynecological cancer patients only. The objective is to determine if prophylactic use of a NPWT system on CDC-defined clean or clean-contaminated, closed laparotomy incisions reduces the incidence of post-operative wound complications.[36] Clinicodemographic variables of interest will be recorded as listed below. All patients enrolled will undergo standard wound closure; this entails fascial closure with PDS suture and a stapled skin closure. Pre and intra-operative details will be collected as described in Table 2. Incidence of inpatient post-operative wound complications will be documented through the use of an inpatient data collection sheet (Appendix C) that will be completed by a provider on the day of day of discharge or post-operative 7, whichever occurs first; these complications are listed in Table 2. Of note, all patients who randomize to the treatment arm are required to have the Prevena system in place for a minimum of 2 days up to a maximum of 7 days. Patients who randomize to the standard dry gauze arm will have their dressing removed on post-operative day 2 (or sooner if clinically indicated). Length of stay will also be captured for each patient. For laparotomy procedures length of stay is routinely a minimum of 2 days [37], thus proving no foreseeable problem with a 2-day minimum placement of the Prevena system nor incurring a greater length of hospital stay. Incidence of outpatient post-operative wound complication will be documented through the use of an outpatient data collection

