sheet that will be completed by a provider at the time of the routine post-operative follow-up visit, which will occur at 30 days +/- 5 days after the day of surgery as well as through ongoing documentation of events as elicited through the institution's standard reporting system to collect information on enrolled patients. At Memorial Sloan Kettering Cancer Center (MSK), this system includes routine post-operative phone calls from nursing staff and 24 hr MD availability via the MSK urgent care center and gynecologic fellows for outpatient telephone communication. Incidence of wound complication as previously defined will be an ongoing assessment throughout the 30 day trial period and not captured as separate endpoints for any particular time.

Table 2: Pre-/Intra-/Post-Operative Patient Assessment

	Pre- operative	Intra- operative	Post- operative (inpatient)	Post- operative (outpatient)
Hemoglobin	Х			
Serum albumin	х			
PTT/PT/INR (optional,	х			
but preferred)				
Indicate if bowel		Х		
resection was				
performed				
Wound type		x		
classification				
Transfusion		X		
Estimated Blood Loss		Х		
Length of surgery		X		
Presence of ascites		Х		

Total IV fluid for first	Х	
24 hours		
Wound infection	X	X
Wound separation	X	X
Wound seroma	X	X
Wound hematoma	X	X
Wound blistering	X	X
Wound contact dermatitis	X	X

Table 3: Timing of Patient Evaluation by Event

	Inpatient	Outpatient
Time of NPWT removal	Day of discharge vs POD 7, whichever occurs 1 ^{st*}	
Post-operative follow-up visit		30 days +/- 5 days post-operative**

*Vac must remain in place for a minimum of 2 days.

**If the patient cannot be seen before POD 35 for a post-operative follow-up visit, a phone call placed by a study investigator may be substituted for the visit (see section 4.2)

POD, post-operative day; NPWT, negative pressure wound therapy.

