13.0 CRITERIAFOR REMOVAL FROM STUDY

Patients will be removed from the study for any of the following reasons but they will not be replaced (see ntention to treat analysis below):

- If at any time the patient is found to be inevaluable for the protocol as designated in the section on Criteria for Patient/Subject Eligibility (e.g., a change in diagnosis), she will be removed from the study.
- If the patient decides to withdraw consent or discontinue participation in the study, she will be removed from the study; however, the Prevena will only be removed for medical reasons and not because the patient is withdrawing from the study.

The following patients will come off study, but they will be included in the analysis:

- If the Prevena Incision Management System is removed prior to 2 days after initial placement, the patient will be included in the analysis as a failure.
- If the patient experiences any grade 4 toxicity as per the MSK Secondary Surgical Events system.

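### The plan does not say what happens to the Prevena system, or how the patient is scored, when discharge comes less than 2 days after placement

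*Combined protocol and SAP*

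**What the plan says.** Section 9.0 gives two wear rules in adjacent bullets. The first is a wear period of a "minimum of 2 days and up to a maximum of 7 days while the patient remains in the hospital post-operatively". The second is that "All Prevena systems will be removed on the day of discharge or post-operative day 7, whichever occurs first". Section 4.2 carries the same pair.

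Section 4.1 says that device-arm patients are "required to have the Prevena system in place for a minimum of 2 days up to a maximum of 7 days". It adds that after laparotomy "length of stay is routinely a minimum of 2 days" and concludes that the minimum should cause no difficulty. In Table 3 the removal timing (discharge or POD 7) carries an asterisk leading to the footnote "Vac must remain in place for a minimum of 2 days".

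Section 13.0 sets the consequence: if the system is "removed prior to 2 days after initial placement, the patient will be included in the analysis as a failure". Section 14.0 repeats this under intention to treat and expects fewer than 5% of enrolled patients to have the system removed that early, without splitting the figure by cause. Gauze patients have the dressing removed on POD 2, or sooner if clinically indicated, and no failure rule is attached.

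**The concern.** If discharge falls less than 2 days after placement, the two wear rules cannot both be met. Section 9.0 describes wear during the hospital stay, and nothing provides for discharge with the device in place. Staff are not told which rule yields. If the device comes off at discharge, Sections 13.0 and 14.0 score a primary failure whatever the state of the wound.

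The clocks add a second uncertainty. Removal is tied to a calendar day (discharge or POD 7), while the failure rule runs from initial placement, and 2 days is not defined as POD 2 or as 48 hours.

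The primary comparison is at stake. The failure rule applies to one arm only, so any patient caught in this gap raises the device-arm rate and leaves the gauze rate unchanged. The dressings are visibly different, so an undefined boundary would also be settled case by case by people who know the assignment.

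**Working it through.** **Step 1. The rules by time of discharge**

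| Discharge | Removal rule | 2-day minimum | Scoring if removed at discharge |
|---|---|---|---|
| POD 1 | Remove | Not met | Failure |
| POD 2, under 48 h from placement | Remove | Met if counted in PODs; not met if counted in hours | Not a failure by POD; failure by hours |
| POD 2 at 48 h or later, up to POD 7 | Remove | Met | Wound outcome |

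Invented example for the middle row: placement at 17:00 on the day of surgery and removal at 11:00 on POD 2 gives 7 + 24 + 11 = 42 hours.

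**Step 2. The plan's own sample size**

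Inputs from Sections 14.0 and 15.2: 10% vs 5%, two-sided type I error 10%, power 80%, 1:1 allocation.

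n per arm = [z(0.95)·√(2·p̄·(1−p̄)) + z(0.80)·√(p1(1−p1) + p2(1−p2))]² / (p1−p2)², with p̄ = 0.075

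= [1.645 × √0.13875 + 0.842 × √0.1375]² / 0.05² ≈ 0.855 / 0.0025 ≈ 342.1, rounded up to 343. The total is 686, as stated.

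**Step 3. Effect of automatic failures**

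Let q be the share of the device arm scored as failed through early removal. The documents do not give q for early discharge, so it is an assumption shown over a range. Take early removal as independent of true complications:

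device-arm rate = 0.05 + 0.95q

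Fixed-sample power at n = 343 per arm is Φ{[(p1−p2)√n − 1.645·√(2p̄(1−p̄))] / √(p1(1−p1) + p2(1−p2))}. For q = 1%: p2 = 0.0595, difference 0.0405, p̄ = 0.07975; (0.750 − 0.630)/0.382 ≈ 0.31, so power is about 62%.

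The two-stage column is from simulation (400,000 trials): pooled Z at 343 and 686 patients; stop at the interim if |Z| ≤ 0.246 or ≥ 2.538; final boundary 1.662; power counted in favour of the device.

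| q | Patients of 343 | Device-arm rate | Fixed-sample power | Two-stage power |
|---|---|---|---|---|
| 0 | 0 | 5.0% | 80.1% | 79.4% |
| 0.5% | 1.7 | 5.5% | 71.7% | 70.8% |
| 1% | 3.4 | 5.95% | 62.3% | 61.2% |
| 2% | 6.9 | 6.9% | 42.6% | 41.3% |
| 3% | 10.3 | 7.85% | 25.5% | 24.6% |
| 5% | 17.2 | 9.75% | 6.2% | 6.0% |

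These figures do not depend on why the device came off early. They price the failure rule for early removal of any cause; early discharge is one contributor of unknown size.

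**The case against.** The best defence is that the plan saw the overlap. The Table 3 asterisk attaches the minimum to the removal timing itself, so a natural reading is that discharge or POD 7 fixes the removal day inside a 2-to-7-day window. Section 4.1 gives a reason to expect few earlier discharges, and nothing in the documents shows that they occur in this population. The plan counts in days and PODs and never gives wear in hours. All of this stands, and it makes the conflict a conditional edge case. It does not close the gap: the footnote restates the minimum without saying what happens at an earlier discharge, and a routine stay of 2 days is not a guaranteed one.

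A reader might infer four stronger things that the documents do not support:

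- That a patient managed fully in line with Section 9.0 is scored as a failure. Section 9.0 also contains the minimum, so removal before it breaks that section.
- That ordinary POD 2 discharges become failures. This needs a 48-hour reading, which is possible but not stated; counted in PODs, they add none.
- That the power losses above are caused by early discharge. They belong to the failure rule, and q is assumed.
- That a patient could go home with the device on. Section 9.0 ties wear to the hospital stay.

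**Conclusion.** The point holds as a gap between sections with a consequence for the primary endpoint. Two wear rules conflict when discharge comes less than 2 days after placement, neither is given precedence, and the resulting removal is an automatic device-arm failure regardless of the wound. The direction is against the device.

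The size cannot be derived from the documents. On the assumptions of true rates of 10% and 5%, independence of early removal from complications, and the stated boundaries, a share of 0.5%, 1% or 2% (about 2, 3 or 7 of 343 patients) would take power from about 79% to about 71%, 61% or 41%. Few patients are needed for an effect, which justifies correcting the wording even if such discharges prove rare.

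**What to change.** 1. Reconcile Sections 4.1 (including Table 3), 4.2 and 9.0 so that one statement covers discharge before the 2-day minimum. Which rule governs is for the clinical team.
2. Put the minimum, the removal day and the early-removal definition in Sections 13.0 and 14.0 on one clock, either PODs or hours since placement.
3. State in Sections 13.0 and 14.0 that a patient whose device is removed because of discharge stays in her randomised arm and is classified by her observed 30-day wound outcome, not as an automatic failure. This concerns scoring only and does not presuppose that the discharge rule outranks the minimum. Section 13.0 lists early-removal patients as coming off study, so it should also say that their 30-day assessment is still collected.
4. Make sure that placement and removal times are captured. The data forms in Appendix C are listed by title only and may already do this.

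The cost is wording in five sections and, at most, two time fields. No extra patients are needed, and the 30-day visit is already routine.

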12.0 CRITERIA FOR THERAPEUTIC RESPONSE/OUTCOME ASSESSMENT

The primary outcome is the observed reduction of wound complications which includes at least one of the following:

- Wound separation as diagnosed by gross observation
- Wound seroma or hematoma as defined by the clinical or radiographic presence of fluid or blood collection in wound
- Wound infection as defined by the presence of purulent discharge requiring exploration and/or cellulitis requiring the use of antibiotics.

Secondary outcomes of wound blistering and contact dermatitis as related to adverse effects of either dressing.

Grading for complications will be captured as per the published MSK Secondary Surgical Events system (Appendix D) and documented for all cases of wound complication.

13.0 CRITERIAFOR REMOVAL FROM STUDY

Patients will be removed from the study for any of the following reasons but they will not be replaced (see ntention to treat analysis below):

- If at any time the patient is found to be inevaluable for the protocol as designated in the section on Criteria for Patient/Subject Eligibility (e.g., a change in diagnosis), she will be removed from the study.
- If the patient decides to withdraw consent or discontinue participation in the study, she will be removed from the study; however, the Prevena will only be removed for medical reasons and not because the patient is withdrawing from the study.

The following patients will come off study, but they will be included in the analysis:

- If the Prevena Incision Management System is removed prior to 2 days after initial placement, the patient will be included in the analysis as a failure.
- If the patient experiences any grade 4 toxicity as per the MSK Secondary Surgical Events system.

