The primary objective analysis of our study will be performed via a two sample test for binomial proportions to compare the difference in proportions between the 2 arms at a type I error of 10%. We will also estimate the proportion of patients with post-op wound complication within 30 days and 90% Confidence interval for each arm assuming binomial proportions. We will perform an intent to treat (ITT) analysis where all patients who were randomized will be included in the analysis in the arm they were randomized to. If the Prevena Incision Management System is removed prior to 2 days after initial placement, the patient will be included in the analysis as per ITT and they will be considered as failures. We expect that <5% of the enrolled patients will have the Prevena system removed prior to 2 days after placement. All patients who were randomized will be evaluable for the analysis except patients that require abdominal reoperation within 30 days to address a postoperative complication unrelated to the surgical wound or patients whose BMI is less than 40 who are found to have benign pathology following their surgery. These patients will be considered non-evaluable for primary endpoint. Patients that require any surgical intervention within 30 days specifically to address a wound related complication will be considered evaluable. Patients removed from the study for reasons listed in Section 13 will be included in the analysis as per ITT principle. We will continue accrual until 686 evaluable patients are randomized.

Interim Analysis: The study will be terminated if either the futility or efficacy boundaries are crossed at the interim analysis when 343 evaluable patients have been randomized. The boundaries for the Z-test statistic after half patients (n=343) are enrolled and randomized when the interim analysis will occur are +/-0.246 for futility and +/-2.538 for efficacy. At the end of the study the boundaries will be +/-1.662.

This secondary objective analysis will analyze each type of complication separately namely wound infection, separation, and formation of seroma or hematoma, in a logistic model where the outcome is the presence and absence of wound complication and the covariate of

interest is the intervention arm (A or B). This analysis will be hypothesis generating as we expect very low rates of each one of these outcomes. P-values will not be adjusted for multiplicity.

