15.2 Randomization

Patients will be randomized (1:1) to either arm A (placement of Prevena wound vac) or arm B (standard dry gauze dressing) immediately after skin closure after all eligibility criteria are established for patients who previously consented to the study. Randomization will be accomplished by the method of random permuted block stratified by BMI > 40 (yes, no). Sealed, opaque, non-resealable envelopes containing the assignment form will be used.

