18.0 INFORMED CONSENT PROCEDURES

Before protocol-specified procedures are carried out, consenting professionals will explain full details of the protocol and study procedures as well as the risks involved to participants prior to their inclusion in the study. Participants will also be informed that they are free to withdraw from the study at any time. All participants must sign an IRB/PB-approved consent form indicating their consent to participate. This consent form meets the requirements of the

Code of Federal Regulations and the Institutional Review Board/Privacy Board of this Center. The consent form will include the following:

- 1. The nature and objectives, potential risks and benefits of the intended study.
- 2. The length of study and the likely follow-up required.
- 3. Alternatives to the proposed study. (This will include available standard and investigational therapies. In addition, patients will be offered an option of supportive care for therapeutic studies.)
- 4. The name of the investigator(s) responsible for the protocol.
- 5. The right of the participant to accept or refuse study interventions/interactions and to withdraw from participation at any time.

Before any protocol-specific procedures can be carried out, the consenting professional will fully explain the aspects of patient privacy concerning research specific information. In addition to signing the IRB Informed Consent, all patients must agree to the Research Authorization component of the informed consent form.

Each participant and consenting professional will sign the consent form. The participant must receive a copy of the signed informed consent form.

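### Section 13.0, read literally, bars removal of the Prevena at a withdrawing patient's request, and the plan leaves unclear whether patients whose device comes off before 2 days are still followed for their wound outcome

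*Combined protocol and SAP*

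**What the plan says.** **Withdrawal.** Section 13.0 (Criteria for Removal from Study) first sets the study status: "If the patient decides to withdraw consent or discontinue participation in the study, she will be removed from the study". It then adds that "the Prevena will only be removed for medical reasons and not because the patient is withdrawing from the study". Section 18.0 (Informed Consent Procedures) lists among the contents of the consent form: "The right of the participant to accept or refuse study interventions/interactions and to withdraw from participation at any time". Section 17.0 adds that a patient may withdraw at any time without prejudice.

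**Timing.** Under Section 15.2, randomisation takes place "immediately after skin closure after all eligibility criteria are established for patients who previously consented to the study". Section 9.0 has the device applied straight after closure. It stays on for 2 to 7 days and comes off at discharge, or on day 7 if that is earlier.

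**Early removal.** A second list in Section 13.0 opens: "The following patients will come off study, but they will be included in the analysis". Its first item covers a device that is "removed prior to 2 days after initial placement, the patient will be included in the analysis as a failure". Section 14.0 (Biostatistics) repeats that "the patient will be included in the analysis as per ITT and they will be considered as failures", and gives the expected frequency: "We expect that <5% of the enrolled patients will have the Prevena system removed prior to 2 days after placement".

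**The concern.** Two linked points arise.

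The first is the patient's position. She consents before surgery and is allocated after skin closure, so the device is already on when she first learns her arm. From then on, asking for its removal is the only way she can refuse it. The clause makes medical need the sole ground and expressly sets withdrawal aside. A site that follows the sentence as written would keep the device on a patient who has left the study and wants it off.

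The second is the data. Early removal is scored as failure, and only arm A has a device to remove. Gauze may come off before day 2 for clinical need with no such penalty (Sections 4.1 and 4.2). If going off study also ends outcome collection, nobody could tell how much of the arm A rate comes from observed wound complications and how much from the scoring rule. The secondary analysis would suffer too, because it models infection, separation and seroma or hematoma separately, and a generic failure has no type. Safety reporting would not fill the gap: Section 17.2 exempts grade 1 to 4 wound endpoint events from SAE reporting.

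**Working it through.** **Part 1: the clause (textual, no arithmetic)**

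1. Grounds for removal stated in the protocol: the schedule (discharge or day 7), side effects that are severe or do not settle (risk table after Section 10.0), and, for a withdrawing patient, medical reasons only (Section 13.0).
2. A withdrawing patient with no medical reason who asks for removal before the scheduled day fits none of these. Sections 13.0 and 14.0 foresee removal before 2 days but give no rule for a request.
3. Section 18.0 grants a right to refuse study interventions, and the device is the study intervention. Taken literally, the two sections give opposite answers for this patient.
4. No rate of requested removal is documented, so this part cannot be sized. Exposure is limited to arm A and to at most 7 days per patient.

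**Part 2: the failure rule**

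Inputs: rates of 10% and 5%, two-sided type I error 10%, power 80%, total 686 (Section 14.0); 1:1 allocation (Section 15.2); early removal under 5% (Section 14.0).

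The plan's own figure reproduces. With pooled variance and no continuity correction:

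n = [1.645 × √(2 × 0.075 × 0.925) + 0.842 × √(0.10 × 0.90 + 0.05 × 0.95)]² / 0.05² ≈ 342.1, rounded up to 343 per arm, 686 in total.

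True events expected in arm A at the design rate: 343 × 0.05 = 17.15.

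Ceiling on early removals:
- if the percentage refers to arm A: 17/343 = 4.96%, so 17 patients;
- if it refers to all enrolled: 34/686 = 4.96%, so 34 patients, all necessarily in arm A.

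For k early removals, suppose their true complication rate is also 5%. Then 0.05k have a real event, 0.95k are imputed failures, and the recorded arm A rate is (17.15 + 0.95k)/343.

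| k | share of 343 | true events among k | imputed failures | recorded arm A rate |
|---|---|---|---|---|
| 3 | 0.87% | 0.15 | 2.85 | 20.00/343 = 5.8% |
| 7 | 2.04% | 0.35 | 6.65 | 23.80/343 = 6.9% |
| 17 | 4.96% | 0.85 | 16.15 | 33.30/343 = 9.7% |
| 34 | 9.91% | 1.70 | 32.30 | 49.45/343 = 14.4% |

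The documents give no complication rate for early removals. Let it be q, and hold the arm's true events at 17.15. With k = 17 the imputed failures are 17 × (1 − q). The values of 20% and 50% below are illustrative.
- q = 5%: 16.15 imputed, recorded rate 9.7%
- q = 20%: 13.60 imputed, (17.15 + 13.60)/343 = 9.0%
- q = 50%: 8.50 imputed, (17.15 + 8.50)/343 = 7.5%

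**The case against.** **On the clause.** There is a benign reading: leaving the research is one thing and clinical care another, so a marketed, FDA-approved dressing need not come off merely because participation ends. The general rights in Sections 17.0 and 18.0 would then govern a separate request. Many real requests would also be medical, since the risk table lists pain, discomfort and skin reactions. She can also decline or withdraw before skin closure. This much stands: a reader might infer that the trial means to deny removal to patients who ask, and the documents do not establish that. The consent form and Appendices A and B were not available and may settle it. What remains is that the sentence says only, and makes no exception for a request.

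**On follow-up.** A reader might infer that the 30-day outcome of early-removal patients is not collected. The plan does not say so. Sections 4.2 and 9.0 end follow-up when a wound event is documented, and early removal is not among the listed events. Section 10.0 collects diagnoses in both arms through day 30 without exception. Patients with grade 4 toxicity sit under the same off-study heading with no failure rule, and analysing them presupposes that their outcomes are available. This objection also stands in part: going off study is undefined, which puts the outcome at risk but does not show that it is lost.

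**On the figures.** The failure rule is prespecified and works against the device. The counts are ceilings under stated assumptions, so 9.7% should not be read as a forecast. Removals prompted by bleeding or a deteriorating wound would plausibly have a higher complication rate, hence fewer imputed failures.

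**Conclusion.** The concern holds in a limited form, as a cheap improvement.

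1. Taken literally, the withdrawal clause in Section 13.0 conflicts with the right described in Section 18.0. The harm is unquantified and bounded by the short wear time. An intention to override patients is not shown.
2. The plan leaves open whether observed wound outcomes are kept for patients scored as failures because of early removal, a rule that can touch only arm A. At the plan's own ceiling, the rule could contribute nearly as many failures as the true events expected in that arm. That size rests on three assumptions: the percentage refers to arm A, removals reach the ceiling, and early removals carry the design complication rate. A higher complication rate among them shrinks the effect; the all-enrolled reading of the percentage doubles the ceiling.

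The figures justify a sensitivity analysis. They say nothing about the size of the withdrawal problem, and they do not show that the primary failure rule should be dropped.

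**What to change.** 1. Reword the clause in Section 13.0, for example: *Withdrawal does not by itself require removal, but the device will be removed at the patient's request after advice on any medical risk.* Check that the consent form agrees.
2. In Section 13.0, do not take a patient off study solely because the device came off before 2 days. Unless she withdraws consent for data collection, follow her to day 30 ± 5, and record the date and reason of removal.
3. In Section 14.0, keep the failure rule for the primary analysis and add one sentence specifying a sensitivity analysis that uses observed wound outcomes for these patients.

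Cost: one clause and one list item in Section 13.0, one sentence in Section 14.0, a date-and-reason field on the data form if it is not already there, and a consent form check. The sample size, boundaries and primary analysis do not change. The downside is possibly a few more early removals in arm A, with those before 2 days still scored as failures in the primary analysis, and follow-up of a small number of patients through a visit or call that is already routine.
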